guidelines, outside of this study protocol can commence after the collection of the post-Kevetrin treatment biomarker samples (collected on Day 21±1 day).

The patient population recruited into this study includes those ovarian cancer patients that have platinum resistant/refractory disease, defined as disease progression/relapse within 6 months following the last administered dose of platinum therapy (resistant), or lack of response or disease progression while receiving the most recent platinum based therapy (refractory), respectively. Patients may or may not have had additional treatment (e.g., Doxil) prior to entry in this study.

A total of approximately 10 study participants are planned to be enrolled in two cohorts of approximately 5 subjects per cohort, with enrollment in a sequential, dose-escalating fashion. Investigators and subjects will be aware of the treatment cohort into which they are recruiting. Cohort details and the planned doses are listed below:

Cohort 1 (n=5) Kevetrin Cycle

Kevetrin 250 mg/m² IV per dose every other day (q.o.d.)/ 3 doses per week (750 mg/m² per week), for 3 weeks (single cycle; total 9 doses)

Follow-up

For 3 weeks after Kevetrin treatment ends

Cohort 2 (n=5) Kevetrin Cycle

[figure not shown]
Kevetrin 350 mg/m² IV per dose every other day (q.o.d.)/ 3 doses per week (1050 mg/m² per week), for 3 weeks (single cycle; total 9 doses)

Follow-up

For 3 weeks after Kevetrin treatment ends

Cohorts 1 and 2 will be conducted in a sequential fashion, with safety data from cohort 1 evaluated by an independent Data Monitoring Committee (DMC). The DMC will make appropriate recommendations based on the available safety data as regards the intent of progressing to the higher dose cohort 2.

Study Design Schematic

If 2 of the 5 subjects in cohort 1 experience a dose-limiting toxicity (DLT) adverse event, the DMC will consider reducing the Kevetrin dose regimen for cohort 2 by 25%.

Dependent on the DLT adverse events experienced, the dose in cohort 1 may be repeated, or reduced. If no new or unexpected safety concerns are identified by the DMC safety review, enrollment of subjects to cohort 2 with a higher dose regimen of Kevetrin will commence.

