If a subject experiences a DLT adverse event during treatment with Kevetrin, treatment with Kevetrin will be stopped and the subject will be appropriately followed-up to document the course of the abnormality until returned to a normal or baseline level, or until the adverse event/abnormality is deemed clinically stable. For any DLT adverse event, the Investigator must immediately notify the Medical Monitor by telephone and follow-up in writing.

For this study, a DLT adverse event is defined as follows, according to the NCI Common Terminology Criteria for Adverse Events (CTCAE) version 4.03:

Hematologic toxicity:

- Grade 3 or 4 febrile neutropenia or Grade 4 neutrophil count decreased of ≥ 7 days' duration
- Grade 4 thrombocytopenia or grade 3 thrombocytopenia complicated by hemorrhage

Nonhematologic toxicity:

- Any grade ≥ 3 nonhematologic toxicity unless there is clear alternative evidence that the adverse event was not caused by Kevetrin
- Grade 3 diarrhea, nausea, or vomiting may be excluded from DLT classification provided that the maximum time limit for supportive measures is 48 hours

A subject studied under this clinical protocol will commence with a screening period of up to 4 weeks, a treatment cycle with Kevetrin (3 weeks), followed by a 3-week follow-up.

Safety and tolerability will be assessed by ascertainment of AEs, physical examinations, and results of clinical laboratory testing, and vital signs assessments. Tumor measurement assessments, by computed tomography (CT) scan, will be taken pre- and post-Kevetrin treatment. Tumor biopsies and ascites fluid (if available), and blood samples for biomarkers will also be collected pre- and post-Kevetrin treatment. Serial blood samples for determination of plasma Kevetrin concentrations will be collected on Study Days 1 and 5, from 2 hours pre-infusion out to 24 hours post-infusion completion.

Any discontinuation of study treatment (Kevetrin) is to be reported by the Investigator to the Medical Monitor. Any subject that discontinues study treatment is to be followed up for (approximately) 3 weeks after the end of treatment. Subjects who withdraw from the study or discontinue treatment for reasons other than a demonstrated intolerance to Kevetrin or a DLT may trigger additional subjects to be enrolled, to obtain 5 completed subjects in each cohort.

Inclusion Criteria:

1. Evidence of a personally signed and dated written informed consent to participate in the clinical study

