Kevetrin will be reconstituted in water for injection (WFI) and placed in a non-PVC infusion bag containing 250mL of 0.9% Sodium Chloride Injection USP (Braun L8002 or equivalent, provided by the site). A low sorbing (PVC-free) IV infusion set equipped with an in-line

0.2- μm pore size filter (CareFusion / Alaris 11532269 or equivalent, provided by the site) will be attached to the non-PVC bag.

Cohort 1: Kevetrin 250 mg/m² IV per dose every other day (q.o.d.)/ 3 doses per week (750 mg/m² per week), for 3 weeks

Cohort 2: Kevetrin 350 mg/m² IV per dose every other day (q.o.d.)/ 3 doses per week (1050 mg/m² per week), for 3 weeks

Nine (9) doses of Kevetrin are to be divided and administered every other day (q.o.d.) as three doses split over each 7-day period, for a single (21-day) treatment cycle.

Doses 1, 2, and 3 are each separated by approximately 48 hours; Dose 4 is administered approximately 72 hours after Dose 3. Doses 5 and 6, and doses 8 and 9 are administered approximately 48 hours after doses 4 and 7, respectively. The separation between doses 6 and 7 is approximately 72 hours.

Each Kevetrin dose is to be administered intravenously over a duration of no less than 180 minutes (3 hours). A pre-medication regimen is recommended for administration within 30 to 60 minutes prior to initiation of each Kevetrin infusion.

Data Analysis:

Details of the statistical methodology for summary and analyses of the data collected in this study will be prepared separately from this protocol in a statistical analysis plan (SAP).

All statistical analyses will be performed using SAS version 9.3 or higher.

Safety endpoints: AEs, SAEs, dosing compliance, any discontinuations from Kevetrin treatment due to toxicities, and changes in laboratory values, vital signs, ECGs, and ECOG performance status, and incidence of clinical laboratory, blood pressure, heart rate, temperature and respiration rate, and ECG abnormalities.

Biomarker endpoints:

- Change from baseline in tumor tissue markers and/or cellular markers (in cells separated from ascites fluid) including, but not limited to, changes in transcriptional and translational pathways leading to anticancer activity such as p53 signaling pathway, miRNA-34a, and other tumor activity markers.
- Change from baseline in ascites fluid markers and/or plasma markers, including CA-125, CCL2, miRNA-25, miRNA-27a, and miRNA-1274b.

Tumor measurement endpoints:

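### After 2 DLTs among 5 subjects at 250 mg/m², the only quantified dose cut, 25% off cohort 2's 350 mg/m², gives 262.5 mg/m², which is 5% above the dose that triggered it

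*Combined protocol and SAP*

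**What the plan says.** All the relevant text is in the protocol synopsis.

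- **Doses.** Under Design and Methodology, cohort 1 is "Kevetrin 250 mg/m² IV per dose every other day", three doses a week for three weeks. Test Product, Dose, and Mode of Administration repeats this and gives the next level as "Cohort 2: Kevetrin 350 mg/m² IV per dose every other day", on the same schedule. No other cohort 2 dose appears.
- **Trigger and response.** Under Study Design Schematic, the trigger reads "If 2 of the 5 subjects in cohort 1 experience a dose-limiting toxicity (DLT) adverse event". The response attached to it is that "the DMC will consider reducing the Kevetrin dose regimen for cohort 2 by 25"%.
- **Alternatives.** The next sentence adds: "Dependent on the DLT adverse events experienced, the dose in cohort 1 may be repeated, or reduced". It gives no size for the reduction.
- **Escalation.** The paragraph ends with a condition, "If no new or unexpected safety concerns are identified by the DMC safety review". When that condition is satisfied, the stated consequence is that "enrollment of subjects to cohort 2 with a higher dose regimen of Kevetrin will commence".
- **Other safeguards.** For a subject with a DLT, "treatment with Kevetrin will be stopped and the subject will be appropriately followed-up to document the course of the abnormality", and the Medical Monitor is told at once. Data Analysis provides for review of cohort 1 by both the independent DMC and the sponsor.

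**The concern.** The paragraph governs the step from cohort 1 to cohort 2 in a trial whose first primary objective is the safety and tolerability of the two regimens. A reader would expect a dose reduction prompted by DLTs to lead to a dose no higher than the one at which they occurred. Here the percentage is attached to the dose not yet given. Because 350 mg/m² is 40% above 250 mg/m², a 25% cut does not cancel the planned increase. If the DMC took up the one numerical option it is offered, the next subjects would receive slightly more drug than the cohort in which 2 of 5 had DLTs.

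The other safeguards do not correct this. Stopping Kevetrin and notifying the Medical Monitor protect the affected subject and do not set the next dose level. The DMC and sponsor reviews are described without a dose limit.

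**Working it through.** **Inputs** (Design and Methodology; Study Design Schematic)

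- Cohort 1: 250 mg/m² per dose, 3 doses per week, 9 doses in total.
- Cohort 2: 350 mg/m² per dose, same schedule.
- Reduction: 25%, attached to the cohort 2 regimen.
- Trigger: 2 of 5 subjects, an observed rate of 2/5 = 40%.

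**1. Reproduce the plan's weekly doses.** 250 × 3 = 750 and 350 × 3 = 1050 mg/m² per week. Both agree with the synopsis.

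**2. Apply the 25% cut to the stated base.** 350 × (1 − 0.25) = 262.5 mg/m² per dose.

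**3. Compare with the dose that triggered the rule.**

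| | Cohort 1 | Cohort 2 after 25% cut | Difference |
|---|---|---|---|
| Per dose (mg/m²) | 250 | 262.5 | +12.5 |
| Per week (× 3) | 750 | 787.5 | +37.5 |
| Over 9 doses (× 9) | 2250 | 2362.5 | +112.5 |

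The ratio is 262.5 / 250 = 1.05 on every row, that is +5%.

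**4. How much of the escalation survives.** The planned step is 350 − 250 = 100 mg/m² (+40%). The cut removes 350 − 262.5 = 87.5 and leaves 12.5.

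**5. Cut needed to return to 250 mg/m².** 1 − 250/350 = 28.6%. Any smaller cut leaves the dose above cohort 1.

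**6. The other possible base.** 250 × (1 − 0.25) = 187.5 mg/m² per dose (562.5 per week; 1687.5 over 9 doses). The two bases give doses 262.5 − 187.5 = 75 mg/m² apart, on opposite sides of 250.

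**7. How often a trigger of 2 or more would be met.** This bears on the cost of the fix and does not measure the defect. The documents give no expected DLT rate, so the true rate p is assumed. With 5 independent subjects, P(2 or more) = 1 − (1 − p)⁵ − 5p(1 − p)⁴.

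- p = 10%: 1 − 0.590 − 0.328 = 8%
- p = 20%: 1 − 0.328 − 0.410 = 26%
- p = 33%: 53%
- p = 40%: 1 − 0.078 − 0.259 = 66%

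**The case against.** The strongest reply is that no stated figure is wrong. The text describes a reduction from the planned cohort 2 dose, never claims that the result is below 250 mg/m², and does cut the increase from 40% to 5%. Read with the next sentence, it can be seen as a graded set of choices: a small step up, a repeat of 250 mg/m², or a lower dose, chosen according to the DLTs seen by a DMC that has all the safety data. This stands in part. The rule is discretionary, lower doses are available, and there is a criterion for choosing among them, though a qualitative one. It does not explain why the only option with a number attached, offered as the response to a 40% observed DLT rate, should exceed the dose at which those DLTs occurred. If 25% below cohort 1 was intended, the text does not say so.

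Three stronger readings are tempting, and the documents do not support them.

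- *Three or more DLTs are left uncovered.* The repeat-or-reduce sentence has no upper count, and reading the trigger as exactly two is strained. Adding the words 'or more' is a tidying change.
- *The higher dose goes ahead whatever the DLT count.* The closing sentence does not mention the count, but the same paragraph makes it a matter for the DMC, whose remit covers the available safety data. This too is a secondary wording point.
- *The plan as a whole has no dose ceiling.* The text available is a synopsis, and a figure is not shown. A fuller rule may exist elsewhere, so the point is limited to what the synopsis says. If there is a fuller rule, the synopsis should agree with it.

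**Conclusion.** The point holds for the quantified option. Applied to the only cohort 2 dose given, the 25% cut leads to 262.5 mg/m², 12.5 mg/m² or 5% above the triggering dose. This rests on one reading, that the percentage is taken off 350 mg/m², and the wording supports that reading directly.

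A reader might infer that subjects would have to receive 262.5 mg/m² after two DLTs, or that the excess is harmful. Neither follows. The DMC is only asked to consider the cut and may repeat or lower the cohort 1 dose instead. A 5% excess is small, and nothing in the documents shows whether it matters clinically. The defect is that the one numerical safeguard points slightly upward when it should hold or lower the dose. It should be corrected before the DMC has to use it.

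**What to change.** Reword the rule along these lines: 'If 2 or more of the 5 cohort 1 subjects have a DLT, the DMC will consider repeating 250 mg/m² or reducing to 25% below the cohort 1 dose (187.5 mg/m²).' This ties the percentage to the cohort 1 dose, states the result in mg/m², and leaves the choice between the two doses with the DMC. Then make clear that the sentence about the higher dose applies when this trigger has not been met. The DLT definition need not change.

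The cost is one reworded paragraph, carried into the DMC's instructions, with no extra subjects or procedures. The real downside is somewhat less DMC flexibility, and possibly no data above 250 mg/m² in a dose-escalation trial when the trigger is met. On the assumed rates in step 7 of the working, that would happen in 8% of trials at a true DLT rate of 10% and in 26% at 20%. Some of those events could be due to the disease, because grade 3 or worse nonhematologic toxicity generally counts as a DLT unless there is clear evidence of another cause.
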